7.3 Significance

This is a non-inferiority trial with a power of 0.8, a non-inferiority limit of 5% and a significance level of P < 0.05.

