7.2 Subject Population(s) for Analysis

We hope to have 60 patients total enrolled in this study (30 Floseal and 30 control). This sample size was chosen to provide the powering listed below. This level of significance is based on a non-inferiority trial. We chose this trial type because we seek to quantify the secondary benefits for this treatment, which is already in use. All randomized subjects will be included in the statistical analysis based on an intention-to-treat protocol.

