Statistical Analysis Plan

Title of Study: Management of Persistent Epistaxis Using Floseal

Hemostatic Matrix

Protocol ID: 6601059

Date of Document: August 22, 2015

Date Modified: October 12, 2018

Sample Size:

An *a priori* sample size was calculated using a non-inferiority limit (d) set at 25%, significance level (α) of 5% and power of 80%. We assumed that success in each group will be approximately 93% based on the literature examining anterior nasal packing in ideal conditions and considering our selection criteria in the Floseal® (Baxter, USA) population. Attrition will be assumed to be 0% due to the short duration of treatment. This should yield 26 participants with 13 patients in each study arm.

Statistical Analysis of Clinical End-points:

This is a non-inferiority trial. A non-inferiority design was chosen due to the anticipated improvement in patient comfort and potential decreased cost thus making the experimental arm a preferred option if non-inferiority can be demonstrated in terms of hemostasis. Further, based on existing literature we do not anticipate a significant difference in terms of efficacy between these two groups. All dichotomous categorical variables will be analyzed by means of the Fisher's exact test. Mean age, CCI and VAS pain scores will be compared using the non- parametric Mann-Whitney U Test.

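### The protocol's 60 patients give about 18–19% power for its 5% non-inferiority limit, not 0.8, and the SAP states a different limit (25%) and size (26)

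*Protocol*

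**What the plan says.** **Protocol (version June 8, 2015).** Section 7.2 plans 60 patients, 30 per arm, and links that number to the power: "This sample size was chosen to provide the powering listed below". Section 7.3 then gives the figures: "This is a non-inferiority trial with a power of 0.8, a non-inferiority limit of 5% and a significance level of P < 0.05". No success rate, no expected difference and no sidedness for alpha are stated. Section 7.5 commits the team to amending and justifying, in the protocol and the final report, any departure from the original statistical plan.

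**SAP.** The header reads "Date of Document: August 22, 2015" and "Date Modified: October 12, 2018". The sample size section describes an a priori calculation using "a non-inferiority limit (d) set at 25%, significance level (α) of 5% and power of 80" percent. It assumes about 93% success in each group and no attrition, and concludes: "This should yield 26 participants with 13 patients in each study arm". Sidedness is again not given. The SAP explains why a non-inferiority design was chosen, but not why 25 points is an acceptable loss.

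**The concern.** There are two problems. First, 30 per arm looks far too small for 0.8 power against a 5-point limit at any plausible success rate. Second, the two documents describe different trials: the limit differs fivefold and the sample size by more than half, with no statement of which applies.

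The limit determines whether Floseal is declared non-inferior, so the same data could succeed under one document and fail under the other. The trial is open-label, and the treating resident judges whether hemostasis is adequate (Protocol 5.1). The SAP was last modified more than three years after its first date, and nothing says what was modified. A reader therefore cannot tell whether the 25% limit was fixed before outcomes were seen. At 93% control success, a 25-point limit tolerates a rise in failure from 7% to 7 + 25 = 32%.

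**Working it through.** **Inputs.** Protocol 7.2–7.3: 30 per arm, limit d = 0.05, power 0.8, alpha 0.05. SAP: d = 0.25, alpha 0.05, power 0.80, success p = 0.93 in both arms (true difference 0), 13 per arm. Because sidedness is not stated, both one-sided 5% and one-sided 2.5% are shown.

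**Formulas.** n per arm = (z_α + z_0.8)² × 2p(1−p) / d². Power = Φ(d/SE − z_α), with SE = √(2p(1−p)/n).

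**1. The SAP's own figure.** 2 × 0.93 × 0.07 = 0.1302.
- One-sided 5%: (1.645 + 0.842)² = 6.18, and 6.18 × 0.1302 / 0.0625 = 12.9, so 13 per arm. This reproduces the SAP's 26.
- One-sided 2.5%: (1.960 + 0.842)² = 7.85, and 7.85 × 0.1302 / 0.0625 = 16.4, so 17 per arm. This does not.

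The SAP's calculation is therefore consistent under this formula only if its alpha is one-sided 5%.

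**2. Size needed for the protocol's 5% limit.**
- One-sided 5%: 6.18 × 0.1302 / 0.0025 = 322 per arm (644 in total).
- One-sided 2.5%: 7.85 × 0.1302 / 0.0025 = 409 per arm (818 in total).

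**3. Power of 30 per arm for a 5% limit.** SE = √(0.1302/30) = 0.0659, and 0.05/0.0659 = 0.759. Then Φ(0.759 − 1.645) = 18.8%, and Φ(0.759 − 1.960) = 11.5%. Exact binomial enumeration agrees on the order of size:

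| Method (p = 0.93, 30 per arm, d = 0.05) | One-sided 5% | One-sided 2.5% |
|---|---|---|
| Normal formula | 18.8% | 11.5% |
| Exact, score test (restricted MLE) | 17.8% | 5.9% |
| Exact, Wald test | 22.0% | 15.8% |

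With the SAP's 13 per arm and a 5% limit, power at one-sided 5% is 12.6% (normal) or 9.3% (exact score).

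**4. Does the borrowed 93% drive this?** Normal formula, equal rates in both arms, 30 per arm, d = 0.05:

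| Common success rate | One-sided 5% | One-sided 2.5% |
|---|---|---|
| 80% | 12.3% | 7.0% |
| 90% | 15.9% | 9.4% |
| 95% | 22.5% | 14.2% |
| 97% | 30.5% | 20.5% |

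The formula reaches 80% at one-sided 5% only near a 99.4% success rate. Conversely, at 93% success, 30 per arm has 80% power for a limit of (1.645 + 0.842) × 0.0659 = 16.4 points, a figure in neither document.

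**5. Effect on the verdict.** Lower limits of the 90% confidence interval for the difference, when both arms perform equally at close to 93%:

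| Result in each arm | Score | Wald | 25% limit | 5% limit |
|---|---|---|---|---|
| 28/30 | −12.6 points | −10.6 points | met | not met |
| 12/13 | −21.9 points | −17.2 points | met | not met |

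By the score method even perfect results fail the 5% limit. The lower limit is then −z²/(n + z²): with z² = 2.706 this is −8.3 points for 30/30 in each arm and −17.2 for 13/13.

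**6. Dates.** The SAP's first date is 75 days after the protocol version. Neither document dates the change in limit or size.

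**The case against.** The strongest reply is that the protocol states neither a success rate nor an expected difference, so the 93% and the zero difference are borrowed from a later document. If Floseal were truly better, 60 patients could be enough. Taking 93% against 75% as an illustration, SE = √((0.93 × 0.07 + 0.75 × 0.25)/30) = 0.0918, and Φ(0.23/0.0918 − 1.645) is about 80.6%. So the combination is not mathematically impossible. But it takes an advantage of about 18 points that neither document states. It also conflicts with the SAP's equal rates and its expectation of no significant difference in efficacy.

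Three narrower points stand:
- The 99.4% figure comes from the normal formula, which is unreliable that close to 100%. By the exact score test, power is about 11.4% at 97% success and about 1.2% at 99.4%. This makes the protocol's claim harder to sustain, not easier.
- The 28/30 example combines the SAP's rate with the protocol's sample size. The 12/13 example uses the SAP's own size and leads to the same conclusion.
- The protocol version provided predates the SAP, so it could not record a later change, and a later version may exist. What can be said is that the version provided shows no amendment.

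The SAP may well be meant to supersede Protocol 7.2–7.3, and it calls its calculation a priori. The undated change is a gap in documentation, not evidence that the margin was chosen after seeing data.

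**Conclusion.** The concern holds. Under the SAP's assumption of 93% success in both arms, the protocol's 60 patients give about 18–19% power for a 5-point limit at one-sided 5%, and less at one-sided 2.5% by each method. No method tried at 93% exceeds 22%. The stated 0.8 cannot be reproduced from any inputs in the documents. Separately, and without borrowing any assumption, the documents give two limits (5% and 25%) and two sample sizes (60 and 26), with no rule for which governs and no justification for the wider limit. Since equal results at the expected rate pass one limit and fail the other, the primary conclusion cannot be interpreted until this is settled.

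**What to change.** 1. State the same four items in both documents: one primary margin with its clinical justification, one sample size, the assumed success rate in each arm, and the sidedness of alpha.
2. Remove the 0.8 power for a 5% limit from Protocol 7.3, or restate it as about 18–19% with 60 patients, 93% success in both arms and one-sided 5%.
3. Record when the margin and sample size changed relative to enrolment and to access to outcome data, and what was modified in the SAP in October 2018. Justify the change in the protocol and the final report, as Protocol 7.5 requires. The trial's status is not known from the documents; if an amendment is no longer possible, put a dated disclosure in the SAP and the report.
4. Report the confidence interval for the difference against the primary margin. For transparency only, say whether it also meets the other stated limit, and word any claim as non-inferior within 25 points if only that limit is met.

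The cost is a protocol amendment and SAP wording. No extra patients are needed if the power is restated rather than the trial enlarged. The price is a less favourable stated power and a qualified claim.

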7.4 Termination Criteria

Termination of this study will occur once we have enrolled the required number of patients or if there are any significant adverse events, which result in a decision by the research team to terminate the study.

7.5 Deviation Reporting

In the case that any changes to the statistical analysis of this trial may arise they will be fully disclosed. Any deviation from the original statistical plan will be amended and justified in the protocol and in the final report.

8 Direct Access to Source Data/Documentation

Throughout the study if direct access data is required for audit or other trial-related monitoring, it can be obtained by written request to [name]. This includes access by any regulatory agency such as the University of Alberta HREB.

9 Quality Control and Quality Assurance

Data from the direct care team will be obtained in paper form and be scanned or otherwise transferred to electronic data kept on the research computer. Interim analysis will be done by the research team to ensure that data collection is continuing as per the protocol. The study coordinator ([name]) will review that data obtained following each patient enrolled in the study and ensure that it is being recorded in compliance with this protocol and good clinical practice requirements.

10 Ethical Considerations

This study will be conducted according to Canadian and international standards of Good Clinical Practice for all studies. Applicable government regulations and University of Alberta research policies and procedures will also be followed.

This protocol and any amendments will be submitted to the University of Alberta HREB for formal approval to conduct the study. The decision of the HREB concerning the conduct of the study will be made in writing to the investigator.

All subjects for this study will be provided a consent form describing this study and providing sufficient information for subjects to make an informed decision about their participation in this study. This consent form will be submitted with the protocol for review and approval by the HREB. The formal consent of a subject, using the HREB-approved consent form, will be obtained before that subject is submitted to any study procedure. This consent form must be signed by the subject or legally acceptable surrogate, and the investigator-designated research professional obtaining the consent.

11 Data Handling and Record Keeping

For confidentiality purposes all data for this study will be coded and de-identified and kept on an encrypted secured database in the personal office of [name].

12 Supplements

Comfort Questionnaire

Patient Name: _____ Researcher Filling out this form: _____

In Person

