3.2 Study Design/Type

This study will be a prospective randomized, open-label clinical trial.

- 1. Otolaryngology Service consulted for persistent epistaxis by Emergency department
- 2. Otolaryngology resident determines whether patient meets inclusion/exclusion criteria for the study
- 3. Informed Consent is obtained and participants are given a chance to ask questions
- 4. Participants will be randomized using a sealed envelope system to either experimental or control group
- 5. Group A receives traditional nasal packing

Group B receives treatment using FloSeal Hemostatic Matrix

- 6. Both Groups are followed to observe the primary endpoint of hemostasis (end of bleeding)
- 7. Hospital care or discharge continues as normal
- 8. Patients are telephoned or visited as inpatients 48 hours later to complete the comfort questionnaire

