3.3 Randomization

This study will be randomized in an allocation concealment fashion with a randomized treatment group already established in an envelope in the treatment room prior to patients being enrolled in the study. The direct care team therefor has no control over the chosen treatment for the patients. Due to the nature of the treatment it is not possible to blind this study to either the direct care team or patient.

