4.4 Treatment of Subjects

The amount of time from patient admission to the emergency department until they are seen by an OHNS resident may be variable due to extraneous circumstances. Upon consult by OHNS if the patient meets the criteria for the study, informed consent will be obtained by a member of the research team (not the direct care team). They will have an opportunity to ask questions and sign the consent form.

a. Participants will be randomized using a sealed envelope system to either experimental or control group

b. Group A receives traditional nasal packing by a trained OHNS resident (merocel gauze)

Group B receives treatment using 5 mL of Floseal Hemostatic Matrix by a trained OHNS resident

c. Both Groups are followed to observe the primary endpoint of hemostasis (end of bleeding)

d. If hemostasis is not promptly achieved (as determined by the direct care team) than additional measures will be taken to arrest bleeding just as they would in any other non-study situation

e. Hospital care or discharge continues as normal

f. Patients are telephoned or visited as inpatients 48 hours later to complete the comfort questionnaire

We will have extra follow-up with these patients to observe the effects of our treatment on patient comfort and allow for the opportunity of a study debrief. This will occur two days following their treatment and should last no more than five minutes over the telephone.

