5.2 Method and Timing

The research team will review the data obtained following each patient enrolled in the study to ensure that the protocol is being followed appropriately and that the primary and secondary endpoints are being appropriately recorded.

6 Assessment of Safety

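### The enrolment stop in protocol 7.4 points to two different totals (60 with a 5% margin, 26 with a 25% margin), and no text bars the team that reviews open-label outcomes from comparing arms before the end

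*Protocol*

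**What the plan says.** **Stopping.** Protocol 7.4: "Termination of this study will occur once we have enrolled the required number of patients or if there are any significant adverse events", the latter being events "which result in a decision by the research team to terminate the study". These are the only two grounds. No stop for efficacy, non-inferiority or futility is written, and 7.4 does not state the number.

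**The number.** The protocol (version June 8, 2015) gives 60 in the Study Summary and, in 7.2, 30 per arm; 7.3 gives a 5% non-inferiority limit, power 0.8 and a 0.05 significance level. The SAP (dated August 22, 2015, modified October 12, 2018) gives 26, or 13 per arm, from a 25% limit, 93% success in each arm, 5% significance and 80% power. Neither document refers to the other's figures or says which governs.

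**Who sees the data.** Protocol 5.2: "The research team will review the data obtained following each patient enrolled in the study to ensure that the protocol is being followed appropriately". The same review covers whether endpoints are properly recorded. Section 9 adds: "Interim analysis will be done by the research team to ensure that data collection is continuing as per the protocol". On masking, 3.3 says "it is not possible to blind this study to either the direct care team or patient". No masking of the research team is described. Section 11 has data coded and de-identified, which hides the patient's identity but not the arm.

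**Disclosure.** Protocol 7.5 commits the trial to disclosing and justifying changes to the statistical analysis.

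**The concern.** A fixed-size trial keeps its error rate because the size does not depend on the results. Here the size is not fixed by the documents taken together: stopping at 26 follows the SAP and stopping at 60 follows the protocol. The people who apply the rule also see each patient's outcome in an open-label trial, and they carry out something called an interim analysis whose content, timing and number are not given. Checking that forms are complete needs no comparison of outcomes by arm, but no sentence excludes one.

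At stake is the credibility of the non-inferiority claim. If the final size could have been chosen with the results in view, the nominal error rate no longer describes the procedure. A later reader could not tell from the documents whether that happened.

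**Working it through.** **1. Reproduce the SAP's number.** Inputs from the SAP: p = 0.93 in both arms, d = 0.25, power 0.80 (z = 0.842), significance 5%. Sidedness is not stated, so both readings are tried.

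n per arm = 2p(1−p)(z_α + z_β)² / d²

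- One-sided 5% (z = 1.645): 0.1302 × 6.183 / 0.0625 = 12.9, so 13 per arm and 26 in total. This matches the SAP.
- One-sided 2.5% (z = 1.960): 0.1302 × 7.849 / 0.0625 = 16.4, so 17 per arm and 34 in total. This does not match.

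The SAP figure therefore implies a one-sided 5% test.

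**2. Try the protocol's number.** The protocol gives no success rate. Assuming the SAP's 93% with the protocol's 5% margin at one-sided 5%: 0.1302 × 6.183 / 0.0025 = 322 per arm. Over assumed success rates from 70% to 99% the need runs from 1,039 down to 49 per arm. At 30 per arm and 93%, the standard error is √(0.1302/30) = 0.0659, and power is Φ(0.05/0.0659 − 1.645) = Φ(−0.886), or about 19%. So the totals are not two roundings of one calculation: 26 follows from its stated margin, and 60 does not follow from its own at any of these rates.

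**3. Error if the text is followed.** If the looks only check data collection and enrolment stops at a number fixed independently of results, there is one test at the end. The added type I error is zero.

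**4. Conditional illustration.** Suppose instead that results by arm were seen at 26 patients and the choice to stop or go on to 60 was made on them, with non-inferiority claimed if either analysis succeeded. Assumptions: margin 25% at both sizes; Farrington–Manning score test, critical value 1.645; control success 93%; Floseal success 93% − 25% = 68%, so that any claim is false.

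| Rule | False non-inferiority |
|---|---|
| Fixed at 13 per arm | 4.0% |
| Fixed at 30 per arm | 5.3% |
| Either 13 or 30 per arm, chosen after seeing results | 7.8% |

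These come from 200,000 simulated trials. Exact enumeration of the binomial outcomes agrees: P(13) + P(30) − P(both) = 4.05% + 5.31% − 1.56% = 7.80%. As a rough check, two normal test statistics with correlation √(26/60) = 0.658, each tested at 1.645, give 8.2% for either.

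**The case against.** The strongest reply is that section 9 states its own purpose. The interim analysis sits under quality control and is meant to confirm that data collection follows the protocol; 5.2 is likewise about recording. No test, look schedule or comparison by arm is mentioned, and the research team's discretion in 7.4 is tied to significant adverse events. All of this stands. A reader might infer planned, unadjusted efficacy looks after each patient. The documents do not support that, and error rates that assume repeated testing do not apply.

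The illustration is also open to challenge. It combines the protocol's 30 per arm with the SAP's 25% margin, and it uses a score test where the protocol names chi-square and the SAP Fisher's exact test. That stands too, and is why the 7.8% is conditional.

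Read alone, the protocol has one total, 60. That does not settle the matter, because the SAP was modified later and gives 26 for the same trial.

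Three further inferences are tempting but not supported:

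- **That the target was cut to 26 in 2018 after results were seen.** The modification date does not say what was modified, the SAP calls its calculation a priori, and nothing shows what was known at the time.
- **That running results steer who is enrolled.** The research team does obtain consent ("informed consent will be obtained by a member of the research team (not the direct care team"), but eligibility lies elsewhere: "Otolaryngology resident determines whether patient meets inclusion/exclusion criteria for the study". Allocation is in a sealed envelope prepared beforehand, and knowing past results does not reveal the next assignment unless the sequence is predictable.
- **That the looks bias the 48-hour comfort questionnaire.** Patients know their treatment in any case, so restricting the data review would not change this.

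**Conclusion.** The concern holds as a contradiction in the stopping number combined with a missing safeguard. The two totals, each with its own margin, are plain in the documents, and 7.4 relies on a number it does not give. The data review is not a planned sequential analysis, and the text as written costs no type I error.

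The exposure is conditional: if results by arm informed the choice between the two totals, a nominal 5% would become about 7.8% under the assumptions in step 4, an excess of 2.5 to 3.8 percentage points over the fixed sizes (7.8 − 5.3 and 7.8 − 4.0). There is no evidence that this occurred, and the documents do not rule it out. The correction is worth making because it is cheap and lets the final error rate be defended.

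**What to change.** - **Protocol 7.4 and the SAP:** state one final enrolment number, the same in both, with the margin and calculation that support it. Align 7.2, 7.3 and the Study Summary.
- **Disclosure under 7.5:** say when and why the total and margin changed, and whether any results by arm were known then, and to whom. This can be done even if data are already collected.
- **Protocol 5.2 and 9:** rename the interim analysis a data-completeness check, and state that outcomes are not compared by arm before database lock.
- **Unchanged:** individual safety review, per-patient checks that the allocated treatment was given, and the adverse-event stop in 7.4.

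The cost is a few sentences of amendment and a short statement of history. The small downside is that no outcome summaries by arm are available until lock.
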